#### 8.6 Urine Pregnancy Test

For Urine Pregnancy Test listing will be provided.

### 9.0 REPORTING CONVENTIONS

#### 9.1 Reporting of Numeric Values

All data will be presented by treatment group. Where appropriate, data will be presented including a total overall column and by visit in addition to treatment group.

**Title: Statistical Analysis Plan-Module I**

 SOP Number:  
 JSS-DM-BIS-01

Current Version Number: 1.0

Previous Version Number: Nil

 Document Date:  
 25MAR2021

?

Summary descriptive statistics will consist of the number and percentage of responses in each category for discrete variables, and the mean, median, standard deviation (SD), SE, median and 95% confidence interval for continuous variables.

Mean and Median values will be reported to one decimal place. Standard deviation, standard error and 95% confidence interval values will be reported to two decimal places.

Percentages will be rounded to one decimal place. Where appropriate, the number and percentage of responses will be presented in the form XX (XX.X %).

All Adverse Events (AE) and Serious Adverse Events (SAE) will be presented: Number of events, Number of subjects and %(n/N) of subjects.

P-values will be rounded to three decimal places. P-values less than 0.001 will be reported as <0.001 in tables. P-values greater than 0.999 will be reported as >0.999.

P value <0.05 will be considered significant.

All listings will be sorted for presentation in order of site number, patient number, date of procedure or event.

All categories of variables will be presented even if there is no data. Zero frequencies are going to be represented as “0 (0.0%)” in reporting of results.

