11.5 Efficacy Analysis

Summary statistics with 95% confidence interval will be presented for PASI, IGA DLQI scores. PASI 75, PASI 50 responses, IGA responders (patients achieving IGA 0 or 1) will be summarized by treatment groups. Change from baseline in DLQI scores will be summarized by the treatment groups. Appropriate parametric or non-parametric tests will be applied to test the significance between active arms vs. placebo. No multiplicity adjustments will be done.

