## 1.0 INTRODUCTION

This Statistical Analysis Plan (SAP) describes a comprehensive and detailed description of strategy and statistical technique to be used to realize the analysis of data for Aurigene Discovery Technologies Limited protocol AUR101-201. (A Phase II, Multicenter, Double-blind, Double-dummy, Placebo controlled, Randomized, Study to Evaluate the Efficacy and Safety of two doses of AUR101 in patients with Moderate-to-Severe Psoriasis (INDUS-2)).

This phase II study is conducted to assess the safety and efficacy of two doses of AUR101 – An oral ROR $\gamma$ T inhibitor for anti-inflammatory disorders in patient with Moderate-to-Severe Psoriasis. The reader of this SAP is encouraged to also read the clinical protocol for details on the conduct of this study and the operational aspects of clinical assessments and timing for completing a patient in this study.

The purpose of this analysis is to evaluate early trends of efficacy signals arising from this Phase II study which can help to plan AUR101 clinical development program. The planned analyses identified in this SAP can be used for amendment of current protocol to change the sample size, manuscript writing or presentation at conferences, and/or regulatory submissions. In addition, exploratory analyses not necessarily identified in this SAP may be performed to support the clinical development program. Any post-hoc, or unplanned, analyses not identified in this SAP performed will be clearly identified in the respective report.

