### 5.1 Sample Size Determination

AUR101 doses will be tested versus placebo with respect to the primary endpoint (PASI 75 response). A sample size of 25 in each of the three arms will provide an 80% power with a one-sided Type I error of 0.05, if the true placebo response rate is 7% and the response rate on investigational arm(s) is 35%. The sample size is increased to 30 to account for ~ 15-20% dropouts over the study period. Placebo response rates from previous studies was 4-7% in most of the studies in similar patient population. No multiplicity adjustments were considered in the sample size calculation as it is a POC study.

A subset of approximately 25 consenting patients will participate in the pharmacokinetic part in addition to main study.

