## 7.0 EFFICACY ANALYSES

### 7.1 Primary Efficacy Analysis

Summary statistics with 95% confidence interval will be presented for PASI. Comparison of percentage of patients achieving at least 75% reduction from Baseline

	JSS Medical Research India Private Limited Data Management		
Title: Statistical Analysis Plan-Module I			
SOP Number: JSS-DM-BIS-01	Current Version Number: 1.0	Previous Version Number: Nil	Document Date: 25MAR2021

PASI score (PASI-75) to Week 12 between treatment arm and placebo will be evaluated using Chi-square/Fisher's exact test with responder and non-responder psoriasis type. Also, 95% CI for the responders within treatment will be evaluated by using Clopper-Pearson method and 95% CI for treatment difference will be evaluated by using Miettinen-Nurminen method.

Additional sensitivity analysis will be tested by using Cochran-Mantel-Haenszel (CMH) test after adjusting the sites and baseline PASI score. The analysis will be performed on efficacy population. No multiplicity adjustments will be done for the primary analysis.

Two sets hypotheses will be tested,

1.  $H_0: P_1=P_0$  vs  $H_1: P_1 \neq P_0$
2.  $H_0: P_2=P_0$  vs  $H_1: P_2 \neq P_0$

Where,  $P_0$ ,  $P_1$  and  $P_2$  are the proportion of responders in placebo, 400 mg and 600 mg arms, respectively. Since, both hypotheses will be tested separately, no multiplicity adjustment will be done.

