## 7.2 Secondary Efficacy Analysis

Comparison of percentage of patients achieving at least 75% reduction from baseline PASI (PASI-75) score at 4 and 8 weeks between test and placebo will be evaluated using Chi-square/ Fisher's exact test with responder and non-responder psoriasis type. Also, 95% CI for treatment and for treatment difference will be evaluated by Clopper-Pearson method and Miettinen-Nurminen method, respectively.

Comparison of percentage of patients achieving at least 50% reduction from baseline PASI (PASI-50) score at 4, 8 and 12 weeks between test and placebo will be evaluated using Chi-square/ Fisher's exact test with responder and non-responder psoriasis type. Also, 95% CI for treatment and for treatment difference will be evaluated by Clopper-Pearson method and Miettinen-Nurminen method, respectively.

Comparison of percentage of patients with Investigator Global Assessment (IGA) scores of 0 or 1 at 4, 8 and 12 weeks of treatment (end of treatment) between test and placebo will be evaluated using Chi-Square test. Also, 95% CI for treatment and for treatment difference will be evaluated by Clopper-Pearson method and Miettinen-Nurminen method, respectively.

	JSS Medical Research India Private Limited Data Management		
Title: Statistical Analysis Plan-Module I			
SOP Number: JSS-DM-BIS-01	Current Version Number: 1.0	Previous Version Number: Nil	Document Date: 25MAR2021

?

Absolute and percent change of PASI score at visit 4, 8 and 12 from baseline will be computed using given formula:

$$\% \text{Change of PASI Score for time T} = \frac{(\text{PASI score at T} - \text{PASI score at baseline})}{\text{PASI score at baseline}} * 100$$

where time T can be week 4, week 8 and week 12.

Summary statistics of absolute & percent change from baseline in PASI score at week 4, 8 and 12 will be presented as n, mean median, SD, SE and 95% confidence interval for mean. Comparison of percent change in PASI scores from baseline to week 4, week 8 and week 12 between treatment groups i.e., from AUR 400mg to placebo and AUR 600mg to placebo will be analyzed using analysis of covariance (ANCOVA) model with baseline scores included as a covariate.

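### SAP 9.1 labels every p-value below 0.05 significant, including unadjusted secondary, additional and subgroup tests that should be called nominal

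*SAP*

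**What the plan says.** SAP 9.1 states, for all reporting, "P value <0.05 will be considered significant". It names no endpoint class.

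The tests it governs are spread over several sections:

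- **Primary.** SAP 7.1: "Two sets hypotheses will be tested", each dose against placebo, two-sided, for Week 12 PASI 75.
- **Secondary.** SAP 7.2 prescribes comparisons for seven endpoints by visit, for example "Comparison of percentage of patients achieving at least 50% reduction from baseline PASI (PASI-50) score at 4, 8 and 12 weeks between test and placebo". It sets no order, no dependence on the primary result and no key secondary.
- **Additional and subgroup.** SAP 7.3 adds visits, DLQI thresholds, PASI 90, PASI 100 and pooled doses. SAP 7.4 adds subgroups.

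On multiplicity, Protocol 11.5 says "Appropriate parametric or non-parametric tests will be applied to test the significance between active arms vs. placebo" and in its next sentence states that multiplicity will not be adjusted for. SAP 7.1 repeats this for the primary analysis. SAP 5.1 gives proof of concept as the reason, though only for the sample size. SAP 2.5 also describes a proof-of-concept study.

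SAP 3.2.5 places PASI 90 and PASI 100 under an exploratory heading. The seven secondary endpoints carry no exploratory or nominal label.

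On use, SAP 1.0 says: "The planned analyses identified in this SAP can be used for amendment of current protocol to change the sample size, manuscript writing or presentation at". The sentence goes on to name scientific meetings and regulatory filings. SAP 1.0 requires only post-hoc or unplanned analyses to be marked as such in the report.

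**The concern.** An unadjusted p-value can be read as descriptive, but a rule that calls it significant turns it into a claim. Under SAP 9.1 a trial that misses Week 12 PASI 75 could still report significant efficacy at another visit, on another endpoint, at one dose or in a subgroup. Because these analyses are planned, SAP 1.0 attaches no caveat to them.

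The endpoints are also related to one another, so chance findings tend to arrive in groups and can look like a consistent pattern. What is at stake is how the secondary results are read in a publication or submission; the primary analysis is unaffected.

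**Working it through.** **1. The plan's own figure.** The documents state no family-wise error rate. Their one error-related calculation is in SAP 5.1: "A sample size of 25 in each of the three arms will provide an 80% power with a one-sided Type I error of 0.05". It assumes response rates of 7% on placebo and 35% on active treatment. With a pooled rate of (0.07 + 0.35)/2 = 0.21:

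- standard error under the null = √(2 × 0.21 × 0.79 / 25) = 0.1152
- standard error under the alternative = √((0.07 × 0.93 + 0.35 × 0.65) / 25) = 0.1082
- power = Φ((0.28 − 1.645 × 0.1152) / 0.1082) = Φ(0.84) = 79.9%

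The figure is reproduced. It concerns one dose comparison on the primary endpoint, so nothing in the sizing covers the secondaries. It is one-sided, whereas SAP 7.1 tests two-sided; at two-sided 0.05 the same formula gives 69% with 25 per arm and 77% with 30. That mismatch is a separate matter.

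**2. Number of tests.**

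- Secondary (SAP 3.2.2 and 7.2): PASI 75 at 2 visits; PASI 50, IGA 0/1, percent change in PASI, change in IGA, change in BSA and change in DLQI at 3 visits each. 2 + 6 × 3 = 20 endpoint-visits; × 2 doses = **40**.
- Additional (SAP 7.3): PASI 75 and 50 at Weeks 2, 6, 14 (12); PASI 90 (12); PASI 100 (12); IGA responders (6); four change scores (24); DLQI 5-point reduction (12); DLQI 0/1 (12); pooled doses (12). Total **102**.
- Subgroup (SAP 7.4, items with a named test): PASI responders 4 × 3 visits × 2 doses × 4 subgroups = 96; PASI change 24; IGA responders 24; head and neck 24. Total **168**.
- 102 + 168 = **270**. Of these, PASI 90/100 account for 24 + 6 (pooled) + 48 (subgroups) + 12 (head and neck) = **90**.

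The counts assume a separate test per dose. SAP 7.2 makes this explicit for percent change in PASI. For change in IGA, BSA and DLQI it speaks only of treatment groups; one three-arm test each would reduce 40 to 11 × 2 + 9 = 31. In the other direction, PASI and IGA are rated by both the investigator and the independent dermatologist, and the protocol synopsis fixes precedence only for the primary endpoint, which could raise the count.

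**3. Chance of at least one p<0.05 among the 40, with no drug effect.** Inputs: two-sided 0.05 (|z| > 1.96); 1:1:1 allocation with a shared placebo arm, so the two dose comparisons correlate at (1/n)/(2/n) = 0.5; a common correlation r between endpoint-visits, which is **assumed**. If all 40 were independent the rate would be 1 − 0.95^40 = 87%. Simulating 40 normal test statistics over 40,000 trials for each r gives:

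| r (assumed) | Either direction | Favouring AUR101 |
|---|---|---|
| 0.5 | 64% | 34% |
| 0.7 | 47% | 24% |
| 0.8 | 37% | 19% |
| 0.9 | 27% | 13% |

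Repeating the ends with 200,000 trials gave 63.5% and 33.6% at r = 0.5, and 26.6% and 13.3% at r = 0.9. Against the one-directional nominal 2.5%, the favourable rate is 13.3/2.5 = 5 to 33.6/2.5 = 13 times larger.

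**4. Clustering.** The expected number of favourable false positives is 40 × 0.025 = 1 whatever the correlation. When at least one occurs, the average number is therefore 1/0.34 = 2.9 to 1/0.13 = 7.7.

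**5. Check with binary endpoints.** A patient-level simulation used 25 or 30 per arm, four underlying scales at three visits, assumed null response rates, visit correlations of 0.5–0.9 and endpoint correlations of 0.3–0.9. Either-direction rates were 30–64% with Fisher's test and 42–74% with chi-square; favourable rates were 15–44% over both tests. The inflation is not an artefact of treating every endpoint as continuous.

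**The case against.** The strongest reply is that nothing is concealed. Protocol 11.5 declares non-adjustment directly after listing PASI, IGA and DLQI analyses, so the statement covers secondaries as well as the primary. SAP 1.0 gives the purpose as looking for early efficacy signals, and the trial is a small Phase II proof-of-concept study with one named primary endpoint at one visit. Strict family-wise control over secondaries is a design preference here. This stands, and it means that leaving the p-values unadjusted is not the fault.

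It does not rescue SAP 9.1. Saying that error is uncontrolled and then calling every result below 0.05 significant are in tension, and SAP 1.0 allows the outputs to travel beyond internal planning.

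Three stronger readings are tempting, and the documents do not support them:

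- That no exploratory label exists. SAP 3.2.5 supplies one for PASI 90 and PASI 100, about 90 of the 270 further tests.
- That an inactive drug would yield a false efficacy claim in up to 64% of trials. That figure includes results favouring placebo; the favourable rate is about half. Neither rate is conditional on the primary failing.
- That a ranked order of secondaries or doses is required. The documents give no basis for any particular order.

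**Conclusion.** The concern holds as a fault of labelling. SAP 9.1 extends the word significant to 40 unadjusted secondary tests and up to about 270 others. With an inactive drug, at least one secondary result favouring AUR101 would earn that label in about 13–34% of trials, or 27–64% counting both directions.

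These rates rest on equal correlations of 0.5–0.9, which the documents do not give, on a separate test per dose, and on treating the tests as continuous. The direction of the conclusion survives changes to each of these; the exact percentages do not. A reader might infer that the plan hides its multiplicity or needs formal control over secondaries. The open statement in Protocol 11.5 and the proof-of-concept purpose rule out both inferences.

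**What to change.** Replace the line in SAP 9.1 with:

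> Statistical significance at 0.05 applies only to the primary PASI 75 Week 12 comparisons in SAP 7.1; all other p-values (secondary, additional, pooled-dose, subgroup) are unadjusted, nominal and descriptive.

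Footnote the tables for SAP 7.2 to 7.4 to match. No testing hierarchy or dose order is needed, and all planned tables stay.

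This leaves the chance of a small secondary p-value unchanged; it removes the claim attached to it. Only the two primary comparisons could then be called significant. With a shared placebo arm, the chance that at least one does so under no effect is about 9.1% in either direction at nominal test size, because the SAP does not adjust across doses. The fix does not alter that.

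The cost is one sentence and some footnotes, with no added patients, data or analyses. The downside is that a secondary, early-visit or subgroup p<0.05 can be reported only as nominal. If treatment codes are already open, a new hierarchy would no longer be credible, but this relabelling would still be available.

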## 10.0 OUTPUT (TABLES, LISTINGS AND GRAPHS) CONSIDERATIONS

The default Tables, Listings and Graphs (TLG) layout will be as follows.

Orientation	All pages should preferably be landscape.
Paper Size	Legal size
Margins	Top: 1 in Bottom: 0.75 in Left: 0.75 in Right: 0.75 in
Font	Font style (preferably Times New Roman) of the Text

**Title: Statistical Analysis Plan-Module I**

 SOP Number:  
 JSS-DM-BIS-01

Current Version Number: 1.0

Previous Version Number: Nil

 Document Date:  
 25MAR2021

Headers	Titles of Table/Listing will be center  Left Sponsor: Study Name: Protocol No:
Footers	Left Analyst Initials: Program Name: Program Run date: time:  Right Datasets Used: Page XXX of YYY

The margin may be reduced as necessary to allow additional rows to be presented, but not at the expense of clarity. In addition, the orientation may be changed to portrait if appropriate. The date format for all presentations will be ‘DDMMYYYY’.

**Title: Statistical Analysis Plan-Module I**

SOP Number:  
JSS-DM-BIS-01

Current Version Number: 1.0

Previous Version Number: Nil

Document Date:  
25MAR2021
